## **Exclusion Criteria**

Patients meeting the following criteria will be excluded from participation in this study:

- Legally incompetent or mentally impaired (e.g., minors, Alzheimer's subjects, dementia, etc.)
- Younger than 18 years of age
- Older than 60 years of age
- Any patient considered a vulnerable subject: pregnant women or fetuses, children, cognitively impaired adults, prisoners
- history of coagulation abnormalities and thromboembolic disease or current abnormal coagulation test values
- history of stroke or acute coronary syndromes within 3 months before surgery
- Preoperative (chronic) anticoagulation therapy
- Abnormal coagulation profile
- Renal failure (serum creatinine > 250 µmol/L [2.83 mg/dL]) or liver cirrhosis
- Sickle cell disease
- ACL reconstruction by a method other than BTB
- Patients with a history of hypersensitivity to Percocet and/or TXA
- •

## Vulnerable Subjects

We do not intend to enroll vulnerable subjects.

#### Subject withdrawal criteria.

Patients are free to withdraw at any time from the study before or after surgery.

## **III. METHODS AND PROCEDURES**

#### **Methods and Procedures**

Patients indicated and scheduled for a BTB ACL reconstruction will be identified from faculty surgeon case logs at the NYU Langone Health, Langone Orthopedic Hospital Sports Medicine Division. After informed consent is obtained, a chart review of patients' medications and past

#### Version 2/26/20

medical histories will be performed based on their electronic medical records to identify any current pain medications or exclusion criteria. In order to maintain the blind, the resident assisting the surgeon will randomize the patient to one of two cohorts using REDCap. Both the resident and surgeon are members of the study team.

- Cohort 1: 1 gram of intravenous tranexamic acid (TXA) before tourniquet inflation and 1 gram of IV TXA before closure of the incision
- Cohort 2: Will not receive TXA.

The resident physician and anesthesiologist will not be blinded to the study, however the surgeon and study team members will remain blinded. Before the surgery begins, the resident will prepare the patient and the TXA will be administered (if assigned) before the tourniquet is placed, at which point the surgeon will be called into the room. The administration of TXA will not prolong the surgery and will not add any additional risks of prolonged anesthesia The surgeon will exit the surgery before closure at which point, the TXA will be administered (if assigned) and the resident physician will close the incision.

Immediate post-operative management will not be affected by this study. All patients will receive a standardized regimen of aspirin for DVT prophylaxis and Percocet for pain management, which is standard of care post-operative treatment.

Information to be recorded pre-operatively includes age, sex, height, weight, BMI, and American Society of Anesthesiology (ASA) classification. Intra-operative information will also be recorded, including operative time, and estimated blood loss. During the surgery, a suction device is utilized to remove excess blood from the surgical site and sucked into the suction drain and placed into a measuring cup. We will measure the perioperative blood loss by looking at the measuring cup and seeing how much blood is inside. The objective is to have the average blood loss of the cohort receiving TXA less than the cohort not receiving TXA. Knee swelling postoperatively will be measured using the swelling ratio. The swelling ratio is defined as the circumference of the operative limb divided by the circumference of the contralateral limb. Pain severity scores at rest will be assessed by use of a visual analog scale (VAS; 0 = no pain, 10 =worst pain imaginable) at 0.5, 1, 1.5, 2, 4, 6, 24, and 48 hours as well as 7 days after surgery. Percocet consumption will be recorded at 24 hours, 1 day, 2 days and 7 days after surgery. Incidence of TXA-related side effects (nausea/vomiting, itching, anxiety, increased thirst, rapid heartbeat) in the first 24 hours will be noted. Time to discharge from the post-anesthesia care unit (PACU) and time to discharge from the hospital will be recorded. Patients will be in the study a duration of two weeks, until their post-operative follow up visit.

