#### Study Design

This will be a single-center, double-blinded randomized controlled study. The study is comparing blood loss and postoperative pain and swelling in two cohorts: patients undergoing BTB ACL reconstruction who receive TXA during surgery and patients who do not receive TXA. The intravenous tranexamic acid will be administered before surgery begins and after the tourniquet is released at the conclusion of the surgery. Blood loss will be measured via measuring the amount of blood in the drain at the conclusion of the surgery. Patients will be asked on postoperative day 1, 2 and 7 to rate their pain according to the VAS scale. Patients will have their knee swelling measured immediately postoperatively and at their one-week follow up visit. The swelling ratio is defined as the postoperative mean circumference of upper pole of patella and lower pole of patella divided by the preoperative values.[9]

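### The resident who assists the surgeon and closes the incision is made the randomizer and left unblinded, although an unblinded anesthesiologist is available and no placebo conceals the infusion

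*Combined protocol and SAP*

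**What the plan says.** Study Design (Section I) sets the label: "This will be a single-center, double-blinded randomized controlled study". The operating detail is in Methods and Procedures (Section III):

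- **Who randomizes:** "In order to maintain the blind, the resident assisting the surgeon will randomize the patient to one of two cohorts using REDCap".
- **Team status:** "Both the resident and surgeon are members of the study team".
- **Who knows the arm:** "The resident physician and anesthesiologist will not be blinded to the study, however the surgeon and study team members will remain blinded".
- **First dose:** "Before the surgery begins, the resident will prepare the patient and the TXA will be administered (if assigned) before the tourniquet is placed", after which the surgeon is called in.
- **Second dose and wound closure:** "The surgeon will exit the surgery before closure at which point, the TXA will be administered (if assigned) and the resident physician will close the" (quote cut one word before its end).
- **Control arm:** "Cohort 2: Will not receive TXA". No placebo, sham infusion or screening of the infusion is described.
- **Primary outcome:** "We will measure the perioperative blood loss by looking at the measuring cup and seeing how much blood is inside". The reader of the cup is not named.

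The plan does not say who administers the TXA, or why the resident rather than the anesthesiologist should hold the allocation.

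**The concern.** The step said to protect the blind gives the allocation to someone who takes part in the operation. The plan evidently accepts that an operator's knowledge of the arm matters, because it keeps the surgeon out of the room at both dosing points. It gives the second operator no such protection.

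Performance bias is at stake. Suctioning, effort at hemostasis and closure technique are operator behaviors that may affect collected blood, swelling and early pain. An assistant who knows the arm could, without intending to, act differently between cohorts or give the surgeon a cue. Blinding whoever reads the cup would not remove this, because the difference would already be in the cup.

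The wording also conflicts with itself. Study team members are said to remain blinded, yet the resident is both a study team member and unblinded.

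**Working it through.** The point concerns roles and has no planned figure to reproduce, so the statements are first set side by side.

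| Role | Knows the arm? | Part in the operation |
|---|---|---|
| Surgeon | No; out of the room at both doses | Operates |
| Resident | Yes; opens REDCap and is declared unblinded | Prepares the patient, assists, closes the incision |
| Anesthesiologist | Yes; declared unblinded | Not described as assisting the surgeon or closing |
| Other study team members | No | Not specified |

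**Step 1. Is the resident's knowledge needed?** Someone must know the arm so that TXA can be given. The anesthesiologist already does. Nothing in the plan requires a second informed person at the operation.

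**Step 2. Would moving the allocation be enough?** Probably not. The resident is preparing the patient around the first dose and takes over at closure around the second. Since control patients receive nothing, the resident could probably see whether an infusion was given, whoever opened REDCap. The missing placebo is therefore a separate route to the same knowledge, and both routes have to be closed.

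**Step 3. Can the resident's conduct reach the primary outcome?** It can, but how far depends on when blood is measured. Methods and Procedures describes blood suctioned during surgery into a measuring cup. Study Design refers to the drain at the conclusion of surgery, and the Data Analysis and Statistical Plan to the suction drain after surgery. Assisting could influence the amount under any of these. Closure could influence it only if collection continues through or beyond closure.

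**Step 4. How large could the effect be?** The documents do not say. For scale only, assume that the resident's knowledge shifts mean blood loss by *b* standard deviations and that TXA has no true effect. Take n = 55 per cohort (Number of Subjects) and the .05 level (Data Analysis and Statistical Plan). The plan does not say whether the test is one- or two-sided; two-sided is assumed. By the normal approximation:

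P(reject) = Φ(b√(n/2) − 1.96) + Φ(−b√(n/2) − 1.96), with √(55/2) = 5.244.

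| Assumed *b* | b√(n/2) | P(reject), normal | P(reject), two-sample t |
|---|---|---|---|
| 0 | 0 | 5.0% | 5.0% |
| 0.10 | 0.524 | 0.0756 + 0.0065 = 8.2% | 8.1% |
| 0.20 | 1.049 | 0.1811 + 0.0013 = 18.2% | 18.0% |
| 0.25 | 1.311 | 0.2582 + 0.0005 = 25.9% | 25.5% |

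With 50 per cohort the normal values are slightly lower: 7.9% at 0.10 and 17.0% at 0.20. These figures show how sensitive a trial of this size is to a systematic shift. They are not evidence that a shift of any given size would occur.

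**The case against.** The strongest reply is that the plan is open about what it does. It names two unblinded people and arranges the surgeon's entry and exit around the doses. The phrase about maintaining the blind can fairly be read as meaning the surgeon's blind. The statement that study team members remain blinded follows an explicit exception for the resident in the same sentence, so it probably means the other members. Study Design does not define double-blinded, so a disclosed unblinded resident does not by itself make the label false. All of this is fair. It reduces the wording conflict to loose drafting, but an operator still knows the arm without a stated need.

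A second reply is that the path to the outcome is conjecture. No section assigns suctioning or hemostasis to the resident, and the lead operator is blinded while operating. This also stands, and it is why no size is claimed. The rejection rates above would apply to any bias of the assumed size in any two-arm trial with this many patients.

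A reader might go further than the documents allow in four ways:

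- **That the resident is unblinded solely because of randomizing.** With no placebo, the infusion could reveal the arm anyway.
- **That the resident is at the table for the whole case.** The text says only that the resident assists the surgeon.
- **That the resident closes unaccompanied.** The text says that the surgeon leaves and the resident closes. It does not say who else is present.
- **That the principal investigator's quarterly review must be limited to coded, pooled data because it is shared with an unblinded anesthesiologist.** The Data and Safety Monitoring Plan does not say that the monitoring anesthesiologist is the one in the operating room, and pooled data may not suit a review of reactions to TXA.

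**Conclusion.** The concern holds in this form: the plan gives the allocation to the resident who assists and closes, leaves that person unblinded although an unblinded anesthesiologist is available, and provides no placebo to hide the infusion. This leaves an avoidable opening for performance bias on an operator-dependent primary outcome.

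The size of the bias is unknown. If a shift of 0.10 to 0.25 SD is assumed with no true drug effect, a two-sided 5% t-test with 55 per cohort would be positive about 8% to 26% of the time. That range rests wholly on the assumed shift. The conclusion also assumes that assisting and closing give the resident some influence on blood collected, swelling or early pain, which is plausible but not spelled out. Sample size, significance level and planned power are unaffected. The change is a worthwhile, low-cost improvement; the point does not show that the result would be invalid.

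**What to change.** In Methods and Procedures, make these changes together:

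1. Have the anesthesiologist, not the assisting resident, open the REDCap allocation.
2. Have the anesthesiologist give control patients a volume-matched intravenous saline injection at the two TXA time points, with TXA and saline in identical masked, coded syringes or bags. The surgeon and the resident are then both blinded.
3. Reword the sentence on blinding to say that only the anesthesiologist is unblinded. This also removes the conflict over the resident's study-team status.

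The second time point is described as after tourniquet release at the end of surgery in Study Design and as before closure in Methods and Procedures. The two descriptions should be reconciled so that the saline follows the same timing as TXA. Separately, the Data and Safety Monitoring Plan should say whether its anesthesiologist is the one in the operating room.

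The cost is a protocol amendment, a change of REDCap user rights, two saline injections per control patient and a little anesthesiologist time for preparing masked doses. No extra staff should be needed if the anesthesiologist prepares them.

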## Protection against Risks

Patients will be screened for any contraindication to aspirin or Percocet use.

The patients will stay in the recovery unit a minimum of 3 hours after surgery as the mean duration of the effect of TXA is 3 hours and be monitored by the recovery unit nurses[3, 12]. Patients will be instructed to call the principal investigator and visit the emergency department if there is are any symptoms of calf swelling or chest pain within the first seven days following surgery.

Additionally, all patients will be de-identified and given a code. Information linking the patient codes to the participants' names and medical record numbers will be stored in a secure location separate from the medical information. Access to the information linking the linkage codes with participant identifiers shall be restricted.

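### The trial is called double-blinded, but the only masking step described is for the surgeon; nothing described keeps patients or recovery staff unaware of the cohort, so the pain data are open to expectation bias

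*Combined protocol and SAP*

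**What the plan says.** Study Design (section I) states: "This will be a single-center, double-blinded randomized controlled study". It does not say which two parties are blinded.

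Methods and Procedures (section III) is the only place that assigns roles: "The resident physician and anesthesiologist will not be blinded to the study, however the surgeon and study team members will remain blinded". Shortly before, the same section says: "Both the resident and surgeon are members of the study team".

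The control arm is one line: "Cohort 2: Will not receive TXA". No placebo, saline or sham infusion appears anywhere in the document.

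The masking procedure concerns the surgeon. At the first dose, "the TXA will be administered (if assigned) before the tourniquet is placed, at which point the surgeon will be called into the room". At the second, the surgeon leaves before closure, TXA is given if assigned, and the resident closes.

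On outcomes, Methods and Procedures says: "Pain severity scores at rest will be assessed by use of a visual analog scale". The readings are at 0.5, 1, 1.5, 2, 4, 6, 24 and 48 hours and at 7 days. Percocet consumption is recorded up to day 7 and side effects over the first 24 hours. The section does not say who collects any of these. Protection against Risks keeps patients in the recovery unit for at least 3 hours, to "be monitored by the recovery unit nurses".

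Pain is part of the Secondary Objective and one of the three statistical endpoints in the Data Analysis and Statistical Plan.

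**The concern.** For a VAS score the patient is the assessor. A patient who knows, or is told, whether a drug meant to reduce bleeding and pain was given can shift the score without any drug effect. So can the manner of whoever asks the question. Percocet use and symptoms such as nausea or anxiety are exposed in the same way.

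The protocol itself supplies the expectation. Under Process of Consent, patients hear the study's purpose and anticipated benefits. Potential Benefits to the Subjects lists those benefits as less pain and less narcotic use.

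The stake is the pain conclusion. The Data Analysis and Statistical Plan makes a verdict of effectiveness depend on statistical significance of the endpoints, and pain is one of them. Keeping the surgeon out of the room does nothing to protect that endpoint.

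**Working it through.** **Step 1: who is masked, and by what means.** The plan has no figure of its own on this point, so the check sets the sections side by side.

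| Role | Status in Methods and Procedures | Masking step described |
|---|---|---|
| Surgeon | Blinded | Out of the room at both doses |
| Study team members | Blinded | None |
| Resident | Unblinded, yet also a study team member | Not applicable |
| Anesthesiologist | Unblinded | Not applicable |
| Patient | Not listed | None |
| Recovery nurses | Not listed | None |
| Collector of VAS, Percocet and side-effect data | Not named | None |

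Two things follow. First, the section contradicts itself: the resident cannot be unblinded and also be one of the team of whom it says "the surgeon and study team members will remain blinded". Second, the document contains no step that would keep a patient or a recovery nurse from learning the cohort.

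**Step 2: which readings fall in the recovery stay.** The minimum stay is 3 hours. The readings at 0.5, 1, 1.5 and 2 hours fall inside it, so 4 of the 9 scheduled VAS readings are taken while recovery nurses are monitoring the patient. The other five (4, 6, 24 and 48 hours, 7 days) fall after that minimum and depend mainly on what the patient has come to know.

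**Step 3: an illustration of size.** The documents give no size for an expectation effect, so the shift is assumed.

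Inputs:
- SD = 2 VAS points. The Data Analysis and Statistical Plan gives an SD of 2 without unit or outcome; applying it to VAS is an assumption.
- n = 50 per cohort. The plan's 50 is read as per cohort because 2 × 50 + 10 = 110, the stated total.
- Two-sided 5% test, one time point, no true drug effect. The plan does not state sidedness.
- Average between-cohort shift b = 0.25 or 0.5 points (assumed).

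Formulas: SE = SD × √(2/n) = 2 × √(2/50) = 0.40. The rejection probability is Φ(b/SE − 1.96) + Φ(−b/SE − 1.96).

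- b = 0: 0.025 + 0.025 = 5.0%.
- b = 0.25: b/SE = 0.625, giving Φ(−1.335) + Φ(−2.585) = 0.091 + 0.005 = 9.6%.
- b = 0.5: b/SE = 1.25, giving Φ(−0.71) + Φ(−3.21) = 0.239 + 0.001 = 24.0%.

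The exact two-sample t-test gives 9.5% and 23.6%. With the full 55 per cohort, the normal approximation gives 10.0% and 25.9%. Almost all of the excess lies in the direction of the expectation.

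**The case against.** The strongest reply is that silence is not a defect. Double-blinded is commonly read to include the patient, and nothing says that patients will be told their cohort. Both doses are given in the operating room, the second during the operation. If the patient is anesthetized at both, a missing saline infusion changes nothing the patient could perceive. A consent form is a natural place to state that patients will not know their group, and the consent pages are not in the copy reviewed.

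Much of this stands. A reader might infer that patients are in fact unblinded, or that the trial lacks the double-blind property it states. The documents support neither. They do not give the patient's state at the first dose, and they describe no disclosure of the cohort.

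A reader might also infer that recovery nurses learn the cohort from a medication record, or that they record the VAS. Neither is stated: the document does not describe how TXA is charted, and it gives the nurses a monitoring role only. If blinded study team members collect the scores, part of the worry falls away.

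Nor are the percentages an estimate of this trial's error rate. They need an average shift between cohorts, and so a good deal of actual unblinding, which is not shown.

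The reply does not remove the gap. Unawareness during surgery does not by itself last through 7 days of pain scores. The one section that assigns roles omits the people who give the pain data and does not name whoever collects them. Its statement about the study team is also contradicted within the section.

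**Conclusion.** The point holds as a gap in the masking, not as proof of unblinding. The plan claims a double blind but describes masking for the surgeon alone. It provides no placebo, no masked record and no named blinded collector, and it places the resident on both sides of the blind. Pain VAS, Percocet use and side-effect data are therefore open to expectation bias. The primary blood-loss outcome is little affected by patient expectation.

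The size of any bias is unknown. The rise from 5% to about 9.5% or 24% is illustrative only. It rests on the assumed SD of 2 VAS points, 50 per cohort, a single time point and assumed shifts of 0.25 and 0.5 points. It does show that a shift that is small on a 0 to 10 scale would matter at this sample size. The change is worth making because it is cheap and protects a named endpoint.

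**What to change.** In Methods and Procedures:

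1. State that patients, recovery nurses and whoever collects VAS, Percocet and side-effect data are blinded, and name the collecting role.
2. Bar the unblinded resident and anesthesiologist from collecting these data, and reword the study-team sentence so that the resident is an explicit exception.
3. Chart the infusion in both cohorts as a masked study drug. Preferably, give Cohort 2 a matched saline infusion at the same two points, prepared by the anesthesiologist, who is already unblinded.

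The cost is minor preparation work for control patients plus protocol and consent wording.

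If the sponsor prefers not to do this, replace double-blinded in Study Design with the roles actually masked, and report the pain results as open to expectation bias. That costs only wording, but gives a weaker design label and a weaker claim on pain.

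### The anesthesiologist knows the cohort, but anesthetic technique and theatre and recovery-unit analgesics are not among the data named for recording, so cohort-dependent analgesia could bias early VAS pain with no planned check

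*Combined protocol and SAP*

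**What the plan says.** All but the last two items below come from section III, Methods and Procedures.

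- **Blinding.** "The resident physician and anesthesiologist will not be blinded to the study, however the surgeon and study team members will remain blinded". The control condition is "Cohort 2: Will not receive TXA"; no placebo infusion is described.
- **Pain readings.** VAS at rest is taken "at 0.5, 1, 1.5, 2, 4, 6, 24, and 48 hours as well as 7 days after surgery". Study Design gives a shorter schedule: "Patients will be asked on postoperative day 1, 2 and 7 to rate their pain according to the VAS scale".
- **Data before surgery.** "Information to be recorded pre-operatively includes age, sex, height, weight, BMI, and American Society of Anesthesiology (ASA) classification". There is also a chart review "to identify any current pain medications or exclusion criteria", which covers drugs the patient already takes, not those given around surgery.
- **Data during surgery.** "Intra-operative information will also be recorded, including operative time, and estimated blood loss".
- **Analgesics after surgery.** "Percocet consumption will be recorded at 24 hours, 1 day, 2 days and 7 days after surgery". The first two times are the same time.
- **Standardization.** Aspirin and Percocet follow a standard regimen, and the study is said not to alter immediate postoperative management. Nothing is said about type of anesthesia, nerve block or other analgesics.
- **Role of pain.** Pain is part of the Secondary Objective and one of the endpoints named in the Data Analysis and Statistical Plan.
- **Analysis.** The same plan compares continuous variables by t-test or Mann-Whitney test, with no covariate.

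**The concern.** Pain in the first hours after surgery depends heavily on what was given in theatre and recovery. One of the people deciding this, the anesthesiologist, knows the cohort. The plan neither fixes the choice before allocation is known nor names it among the data to be collected. If the choice varied with cohort, the unadjusted VAS comparison would mix the effect of TXA with the effect of the analgesia. That could create an apparent TXA benefit or hide a real one, and the planned data set would not let a reader tell which.

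The one perioperative analgesic that is recorded does not help with the early readings, because its first record comes at 24 hours. The statistical plan also requires significance on its endpoints to show that TXA is effective, so the pain comparison carries weight in the trial's conclusion.

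**Working it through.** There is no figure in the plan to reproduce on this point. The check has three parts.

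**1. Readings against records.** The VAS times in Methods and Procedures are 0.5, 1, 1.5, 2, 4, 6, 24 and 48 hours and 7 days. Six of the nine are at or before 6 hours, and all six precede the first Percocet record at 24 hours. The section Protection against Risks keeps patients in recovery for at least 3 hours, so the readings from 0.5 to 2 hours fall within that stay. No named data item covers analgesia specifically in this period.

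**2. Size of a systematic difference.** Inputs:

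- Effect of the technique on VAS: 1 to 3 points (assumed; not in the documents).
- Systematic difference in its use between cohorts: 10 to 30 percentage points (assumed; not in the documents).
- SD 2: given in the Data Analysis and Statistical Plan without naming the endpoint; applying it to VAS is an assumption.
- 50 per cohort: implied by the same section, since 110 less the 10 added for exclusions is 100.

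Formulas:

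- Shift = effect × difference in use.
- Standard error of the VAS difference = 2 × √(2/50) = 0.40.
- Two-sided false-positive rate at one time = Φ(shift/0.40 − 1.96) + Φ(−shift/0.40 − 1.96).

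| Effect on VAS | 10 points' difference in use | 20 points | 30 points |
|---|---|---|---|
| 1 | shift 0.1, rate 5.7% | 0.2, 7.9% | 0.3, 11.7% |
| 2 | 0.2, 7.9% | 0.4, 17.0% | 0.6, 32.3% |
| 3 | 0.3, 11.7% | 0.6, 32.3% | 0.9, 61.4% |

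For the middle cell, 0.4/0.40 = 1, and Φ(−0.96) + Φ(−2.96) = 0.17. With the 55 per cohort to be enrolled, the same cell is 18.2%.

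**3. Chance imbalance.** This is a matter of precision, not bias. With use at 50% and 50 per cohort, the standard error of the difference in use is √(2 × 0.25/50) = 0.10. A chance difference of 10 percentage points is therefore ordinary, and the test's standard error already allows for it. What adjustment can gain is the share of VAS variance due to technique, effect² × p(1 − p) / [4 + effect² × p(1 − p)], where p is the proportion using it and 4 is the remaining variance (SD 2 squared):

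- 2 points, p = 0.5: 1/5 = 20%.
- 1 point, p = 0.5: 0.25/4.25 = about 6%.
- 3 points, p = 0.5: 2.25/6.25 = 36%.
- 2 points, p = 0.9: 0.36/4.36 = about 8%.
- One technique used in all patients: 0%.

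**The case against.** The case on the other side has several parts.

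- **The records may exist.** The intra-operative list is introduced by a word that leaves it open, and the team already reviews electronic records for current pain medication. A reader might infer that analgesia can never be checked. The documents do not support that: anesthesia details might be retrieved from the medical record. What stands is that the plan does not name them or provide for their use.
- **Opportunity is not occurrence.** The documents give no reason why knowing TXA status should change the choice of analgesic. This stands, and it limits the point to an unguarded risk.
- **Chance differences are not bias.** A reader might count any imbalance in nerve blocks as distorting the result. Randomization and the test's error rate already cover chance imbalance; only a cohort-dependent choice is bias. This stands in full.
- **Recovery staff.** A reader might infer that those giving recovery analgesia also know the cohort. Only the resident and anesthesiologist are named as unblinded, and recovery nurses monitor the patients. The documents do not say who decides on recovery analgesia.
- **The early readings may not apply.** Study Design lists days 1, 2 and 7 only. If that schedule governs, the six early readings disappear and the point shrinks to the first day's reading. The nine-time schedule is the detailed one, but the conflict is real.
- **Management is said to be unaffected and Percocet standardized.** Those statements concern care after surgery. They do not cover what is given in theatre.

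**Conclusion.** The point holds as a gap in a secondary endpoint. An unblinded anesthesiologist, six early VAS readings, no named record of anesthetic technique or of theatre and recovery analgesics, and an unadjusted comparison together leave a route to bias with no planned check.

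Its size is unknown. The range of 0.1 to 0.9 VAS points, and the rise from 5% to about 17% for a 0.4-point shift, rest on assumed effects and differences in use, on reading SD 2 as the SD of VAS, and on 50 per cohort. They show what a systematic difference would do, not what is expected.

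A reader might go further and conclude that the early pain results will be invalid, or that the trial's main result is compromised. Neither follows. No differential analgesia is shown, and the Primary Objective is blood loss, which this does not directly affect. The change is worth making because it is cheap, and because a plan entered before allocation cannot be recreated afterwards.

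**What to change.** 1. In Methods and Procedures, have the planned anesthetic technique, including any nerve block, entered in REDCap before the allocation is opened. In the Data Analysis and Statistical Plan, name it as a covariate for VAS up to 24 hours. Because it is fixed before allocation, it is safe to adjust for, and comparing it with what was actually given, by cohort, provides the missing check.
2. Record theatre and recovery-unit analgesics from the anesthesia and recovery records, and Percocet, in non-overlapping periods that separate the early readings, for example 0-6 h, 6-24 h, 24-48 h and 48 h-7 days. This also removes the duplicated 24-hour time. Report these by cohort, but do not adjust for drugs given after allocation, since TXA could itself influence their use.
3. Reconcile the VAS schedules in Study Design and in Methods and Procedures.

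The covariate does not remove bias from choices made after allocation; reporting those drugs by cohort makes such a difference visible. No change in care is proposed. The cost is a few REDCap fields, some wording in the statistical plan and a small data-entry burden.
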